### **3.11 Post-treatment Amyvid PET/CT Scan**

A second Amyvid (Florbetapir-F18) PET scan will be done at 4 months after completion of treatment. Amyvid will be administered at a dose of 370 MBq (10 mCi) administered as a single intravenous bolus in a total volume of 10 mL or less. Following the injection, an intravenous flush of 0.9% sterile sodium chloride will be administered. A 10-minute PET image will be acquired starting 30 to 50 minutes after Amyvid intravenous injection. The patient will be supine and the head positioned to center the brain, including the cerebellum, in the PET scanner field of view. Reducing head movement with tape or other flexible head restraints may be employed. Image reconstruction will include attenuation correction with resulting transaxial pixel sizes between 2 and 3 mm. Amyvid images will be interpreted only by the study designated nuclear radiologist. Analysis will be carried out as previously described. Pre- and post-radiation scans will be presented in random order, with the nuclear radiologist blinded to the order of presentation and patient identity or clinical details.

### **3.12 Stopping Rules**

This study will be stopped for any of the following reasons

- 1) Any patient death attributed to treatment
- 2) Any patient who develops a Grade IV adverse event
- 3) More than 3 of 15 patients who develop a Grade 3 adverse event as per CTCAE v.5.0 in either group
- 4) 50% or more patients in either group have no change or increase in amyloid based on Amyvid PET Scan

- 5) 5 patients that show greater than 4 point deterioration in MMSE in two consecutive cognition evaluations
- 6) 5 patients that show increases greater than 7 on ADAS-Cog scale.

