**Schema**

For Patients with Probable Alzheimer's Disease based on NINCDS-ADRDA Criteria and having MMSE scores of between 10 - 20	
Number of Patients	30
Randomization	N/A
Screening/Baseline Testing	
The following tests/evaluation will be completed prior to initiation of treatment
 
 
1) MMSE
 
2) ADAS-Cog
 
3) History and Physical
 
4) Amyvid PET Scan
 
5) Toxicity Evaluation using CTC version 5.0/RTOG for following sites Skin, Eye, Ear and CNS
 
6) QOL-AD and QUALID assessment
 

Imaging Requirements	An Amyvid PET Scan will be required prior to treatment and at 4 months following completion of therapy. These scans will be read by the study designated board certified nuclear radiologist.
Treatment Procedure	Patients will receive whole brain irradiation using standard external beam techniques. The initial 15 patients will be treated at Dose Level 1 (5 x 200 cGy). If after the last patient in the first treatment group has been followed for 12 months and there have been no events that cause stoppage of the trial, the second group of patients will be enrolled at Dose Level 2 (10 x 200 cGy). All patients will receive 1 treatment per day on consecutive days excluding weekends
Trial Visits and Follow-Up	All patients will be followed as per Study calendar. Scheduled post treatment visits are at 6 weeks 3, 4, 6, and 12 months

Stopping Rules	
This Study will be stopped for any of the following reasons
 
 
1) Any patient death attributed to treatment
 
2) Any patient who develops a Grade IV adverse event
 
3) More than 3 of 15 patients who develop a Grade 3 adverse event as per CTCAE v.5.0 in either group
 
4) 50% or more of patients in either group have no change or increase in amyloid based on Amyvid PET Scan
 
5) 5 patients that show greater than 4 point deterioration in MMSE in two consecutive cognition evaluations
 
6) 5 patients that show mean increases greater than 7 on ADAS-Cog scale.
 

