### 2.2 Secondary Objectives

- 1) Investigate whether or not the intervention with low dose whole brain irradiation changes the recognized progression of Alzheimer's disease through cognitive testing.
- 2) To monitor quality of life parameters.

- 3) Collect information from AMYvid® PET Scans before and after treatment to investigate if there is any correlation between neurocognitive/quality of life scores and changes in amyloid plaque size, number and location.

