### **2.4 Secondary Endpoints**

- 1) Neurocognitive testing will be used to assess changes in cognitive function using the MMSE and ADAS-Cog. The tests will be administered by an appointed, trained site professional at baseline and at 6 weeks, 3 months, 6 months, and 12 months during follow-up.
- 2) Quality of life will be monitored via questionnaires completed by the patient prior to the start of irradiation and at 6 weeks, 3 months, 6 months, and 12 months during follow-up. Specific questionnaires include the QOL-AD and QUALID, which have been established as sensitive measures of various parameters of quality of life.
- 3) A pretreatment and post treatment (4 months) Amyvid PET/CT scan will be carried out to determine if there are any correlations between neurocognitive /QOL test results and amyloid number, size and location and changes after treatment.

[figure not shown]

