### **3.6 Pretreatment Amyvid PET/CT Scan**

Amyvid (Florbetapir-F18) is a radiopharmaceutical compound approved by the FDA as a diagnostic tool in AD. Amyvid binds to amyloid- $\beta$  with a half-life of 110 minutes. The tracer significantly accumulates more in brains of patients with AD particularly in the regions known to be associated with amyloid- $\beta$  deposits [57]. A negative Amyvid scan indicates sparse to no amyloid- $\beta$  neuritic plaques and is inconsistent with a neuropathological diagnosis of AD at the time of image acquisition. A positive Amyvid scan indicates moderate to frequent amyloid neuritic plaques; neuropathological examination has shown this amount of amyloid neuritic plaque is present in patients with AD, but may also be present in patients with other types of neurologic conditions as well as older people with normal cognition. Amyvid will be administered at a dose of 370 MBq (10 mCi) administered as a single intravenous bolus in a total volume of 10 mL or less. Following the injection, an intravenous flush of 0.9% sterile sodium chloride will be administered. A 10-minute PET image will be acquired starting 30 to 50 minutes after Amyvid intravenous injection. The patient will be supine and the head positioned to center the brain, including the cerebellum, in the PET scanner field of view. Reducing head movement with tape or other flexible head restraints may be employed. Image reconstruction will include attenuation correction with resulting transaxial pixel sizes between 2 and 3 mm. Amyvid images will be interpreted only by the study designated board certified nuclear radiologist. The current guidelines for display and interpretation of Amyvid images will be followed (Appendix VII). Briefly, images will be displayed in the transaxial orientation with access as needed to the sagittal and coronal planes. In reviewing the images, all transaxial slices of the brain will be included using a black-white scale with the maximum intensity of the scale set to the maximum intensity of all the brain pixels. The brain slice with the highest levels of image contrast (highest radioactivity signals for Amyvid uptake) will be located and the contrast adjusted appropriately. Image interpretation will be initiated by displaying slices sequentially from the bottom of the brain to the top. Image interpretation is based upon the distribution of radioactive signal within the brain; clinical information is not a component of the image assessment. Images are designated as positive or negative by comparing the radioactivity in cortical gray matter with activity in the adjacent white matter.

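### Stopping rule 4 and secondary endpoint 3 need a change in amyloid, but the only Amyvid read the plan defines is positive or negative

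*Combined protocol and SAP*

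**What the plan says.** Rule 4 in section 3.12 is one of six reasons for which the study will be stopped: "50% or more patients in either group have no change or increase in amyloid based on Amyvid PET Scan". The Schema repeats it: "50% or more of patients in either group have no change or increase in amyloid based on Amyvid PET Scan". The rule also gates escalation. Under Treatment Procedure, the Schema sets this condition for escalating once the first cohort's one-year follow-up is complete: "there have been no events that cause stoppage of the trial, the second group of patients will be enrolled at Dose Level 2".

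Secondary objective 3 (section 2.2) relates cognition and quality of life to "changes in amyloid plaque size, number and location". Secondary endpoint 3 (section 2.4) refers to "amyloid number, size and location and changes after treatment".

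The scan itself is read as follows. Section 3.6: "Images are designated as positive or negative by comparing the radioactivity in cortical gray matter with activity in the adjacent white matter". Section 3.11, on the 4-month scan: "Analysis will be carried out as previously described", with the addition that "Pre- and post-radiation scans will be presented in random order, with the nuclear radiologist blinded to the order of presentation".

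The protocol adopts no SUV ratio, regional score, reference region, minimum change or test-retest margin. SUV ratios and a five-point visual score appear only in the appended Amyvid label (Appendix VII), where they describe the label's own studies. The label also says that a read estimates neuritic plaque density (its section 2.4), and that use for monitoring response to therapy is not established (Limitations of Use). The inclusion criteria in section 3.3.2 do not ask for a positive baseline scan.

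**The concern.** A two-category read at each of two visits can show a decrease in one way only: positive before, negative after. A patient whose amyloid falls but whose scan stays positive is scored as unchanged and counts toward stopping. A patient who is negative at baseline can never show a decrease and always counts toward stopping.

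The wording of rule 4 and the blinded, random-order presentation of the paired scans suggest that a graded comparison may have been intended. If so, the plan does not say what is compared, by how much it must differ, or in which brain regions.

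Rule 4 is a mandatory stop on which Dose Level 2 depends. If the definition is settled after the scans are seen, the escalation decision depends on that choice. A stop after the first cohort would remove all Dose Level 2 safety data. For endpoint 3, the defined read leaves only a comparison of converters with non-converters among at most 15 patients per cohort. No read of this scan gives plaque size or number.

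**Working it through.** **1. The plan's own figures.** The only calculation given for 15 patients is the zero-event upper limit in section 3.1, which is 1 − α^(1/15):
- α = 0.01: 26.4%
- α = 0.05: 18.1%
- α = 0.10: 14.2%

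All three reproduce. No operating characteristic is given for rule 4.

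**2. The trigger.** The cohort is 15 (section 3.1), and 50% of 15 is 7.5, so rule 4 fires when 8 or more patients are not decreased, that is, when 7 or fewer are. If each patient is scored as decreased with probability q, independently, then P(stop) = P(X ≤ 7) with X ~ Binomial(15, q).

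**3. What each read scores.**

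| Patient | Positive/negative read | Graded read (not defined in the plan) |
|---|---|---|
| Positive, falls to negative | decrease | decrease |
| Positive, falls but stays positive | no change: counts toward stop | decrease |
| Negative at baseline | can never decrease: counts toward stop | depends on the measure |

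**4. Same patients, two reads.** The documents give no human rate, so these are assumptions: amyloid falls in 80% of patients, the graded read has no error, and a share s of the falls reaches a negative scan. The graded read has q = 0.8; the positive/negative read has q = 0.8 × s.

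| Read | q | P(stop) |
|---|---|---|
| Graded | 0.80 | 0.004 |
| Positive/negative, s = 25% | 0.20 | 0.996 |
| Positive/negative, s = 50% | 0.40 | 0.79 |
| Positive/negative, s = 75% | 0.60 | 0.21 |

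These figures are for rule 4 alone, one cohort, one look, with all 15 scanned twice. Rule 4 applies to either group. Counting two cohorts with the same q gives 1 − (1 − 0.787)² = 0.95 at s = 50%, against 1 − (1 − 0.0042)² = 0.008 for the graded read. The rule states no minimum number of scans, so earlier looks on fewer patients are possible and are not modelled.

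**5. A graded read needs a margin.** If amyloid does not change, measurement error is symmetric and any numerical fall counts as a decrease, then q = 0.5 and P(stop) = 0.50. Error alone would let the study continue half the time.

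**6. Baseline-negative patients.** Suppose k of 15 are negative at baseline and 60% of the rest convert (assumed). Then P(stop) = P(X ≤ 7) with X ~ Binomial(15 − k, 0.6): 0.21, 0.31, 0.43 and 0.56 for k = 0, 1, 2 and 3.

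**7. A missing scan.** If one patient is dropped from the denominator, the trigger becomes 7 of 14. P(stop) is then 0.85 rather than 0.79 at q = 0.4, and 0.012 rather than 0.004 at q = 0.8. Section 3.9 replaces patients who do not complete radiotherapy but does not mention a missing 4-month scan.

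**The case against.** **Scoring rule 4 on the positive/negative read is an inference.** This stands. The rule's wording reads as graded, and paired blinded reading fits a comparison. But no graded read is defined, and section 3.11 sends the reader back to the method of section 3.6.

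**The probabilities reflect assumed rates.** This also stands. A reader might infer that the swing in P(stop) from 0.996 at 20% conversion to 0.004 at 80% measures the defect. It does not: any rule triggered at 8 of 15 has that curve, however well its measure is defined. What bears on the gap is the difference between the two reads on the same patients. A reader might also see harm in the positive/negative read almost always stopping when amyloid has not changed, but that is what rule 4 asks for.

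**Baseline-negative patients may never be enrolled.** The scan is listed under screening in the Schema, section 3.4 adds a specialist consultation on suitability, section 3.6 calls a negative scan inconsistent with a neuropathological diagnosis of AD, and non-Alzheimer dementia is an exclusion. Some such patients could therefore be screened out. No sentence requires a positive scan, so the possibility remains, but the figures in step 6 are weakly grounded.

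**The DSMB can supply the definition.** Section 5.0 makes it advisory, lets it recommend continuing or modifying, and has it adopt a charter beforehand. The charter is not among the documents and may hold an operational rule. The protocol does not point to one for rule 4, and its own wording is mandatory.

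**The study is descriptive (section 3.1).** That limits the weight of endpoint 3. It does not excuse rule 4, which is a decision rule rather than an inference.

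**Conclusion.** The gap is real. The one read that the plan defines cannot deliver what rule 4 and secondary endpoint 3 ask for. Followed literally, it scores a partial fall as no change and counts it toward a mandatory stop. A graded alternative is suggested by the wording but nowhere specified, and the two can lead to opposite decisions: under the assumptions above, 0.004 against 0.79 when half of the falls reach a negative scan, with 0.21 to 0.996 across shares of 75% to 25%. These figures illustrate the disagreement. They do not predict how likely this trial is to stop.

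The importance rests on the Dose Level 2 gate. Endpoint 3 alone, being secondary and descriptive, would not carry the same weight. A reader might infer that the primary endpoint is compromised. The documents do not support that: its definition, toxicity and adverse events by CTCAE, does not use the scan. The exposure is indirect, through the possible loss of Dose Level 2 safety data.

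**What to change.** - **Measure.** Pre-specify a quantitative change measure from the two scans already planned, for example global and regional cortical SUV ratio. Justify the reference region: the label's ratio uses the cerebellum, and section 3.8.2 puts the entire brain in the irradiated target. A graded visual score would also need justification, because the label describes its own five-point method as not intended for clinical use.
- **Margin.** State what change exceeds test-retest error.
- **Endpoint 3.** Use this measure for endpoint 3, keep the positive/negative read as descriptive, and reword sections 2.2 and 2.4 to global and regional amyloid signal, because the scan does not give plaque size or number.
- **Rule 4.** Reconcile the Schema and section 3.12 with sections 3.6 and 3.11. State which measure the rule uses, what counts as change, and how baseline-negative patients and missing scans are counted. If the DSMB charter already does this, cite it. No stopping threshold is proposed here.
- **Limitation.** State that Amyvid is not established for monitoring response to therapy.

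The cost is protocol wording and some image post-processing, with no extra scan or visit. The downsides are a reference region that must be defended in an irradiated brain, possibly a slightly smaller PET analysis set if baseline-negative patients are left out, and the label limitation, which remains.

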Data Safety Monitoring Board (DSMB)	
This trial will utilize a DSMB consisting of three physicians and one biostatistician who are not directly involved in the trial but who have expertise in radiation, Alzheimer's management, or both.
 
They will meet monthly to review all new data that has been collected on any patient under treatment or in follow up and report quarterly to the IRB.

Treatment Groups	
There will be two dose levels:
 
 
1) 5 x 200 cGy
 
2) 10 x 200 cGy
 

Trial Duration	12 month follow up following completion of therapy for each individual.

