### **2.3 Primary Endpoints**

The primary endpoint will be evaluation of toxicity, adverse events and reportable serious adverse events, i.e. grade 3 or higher, as defined by the NCI Common Toxicity Criteria for Adverse Events (CTCAE v. 5.0). RTOG/EORTC Radiation Toxicity Grading is standard of care at Beaumont Hospital for all radiation patients and CTCAE is the standard for reporting & publications. These criteria comprise of various parameters, including performance status, motor function, sensory function, general mental status, nausea/vomiting, hearing loss, xerostomia, and skin toxicity [51]. The CTCAE are cancer-specific and will be supplemented by information from neurocognitive testing using MMSE and ADAS-Cog. The tests will be administered by an appointed, trained site professional at baseline and at 6 weeks, 3 months, 6 months, and 12 months during follow-up. In the context of radiation oncology, the optimal time period for assessing cognitive impairment is within >6 months to 1 year [52,53].

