### **3.5 Pretreatment Evaluation of Cognitive Status**

Candidate patients for the study will undergo assessment of general and neurologic history, physical and neurologic examinations and administration of the following psychometric or behavioral tests: the Alzheimer's Disease Assessment Scale2r-Cognitive Subscale (ADAS-Cog) and the mini-mental state examination (MMSE).

The mini-mental state examination (MMSE) and the Alzheimer's Disease Assessment Scale Cognitive scales (ADAS-Cog) have been the most widely used in clinical trials of AD treatments. The MMSE is a sensitive, valid and reliable 30-point questionnaire that is used extensively in clinical and research settings to measure cognitive impairment. It is commonly used to screen for dementia. It is also used to estimate the severity and progression of cognitive impairment and to follow the course of cognitive changes in an individual over time; thus making it an effective way to document an individual's response to treatment.

Administration of the test takes between 5–10 minutes and examines functions including registration, attention and calculation, recall, language, ability to follow simple commands and

orientation. The ADAS-Cog test is more thorough than the Mini Mental State Exam, and it primarily measures language and memory. The ADAS-Cog consists of 11 parts and takes approximately 30 minutes to administer. It is suggested that a change of 4 or greater in the MMSE is needed before results can be considered different from random events whilst results changes greater than 7 in the ADAS-Cog have been proposed to represent clinically significant changes.

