### **3.10. Cognitive Assessment and Quality of Life Assessment During Treatment**

The Mini Mental Exam and ADAS-Cog are the two most commonly used tests of cognition in Alzheimer's Disease [58]. After treatment these tests will be administered by study designated, trained professional at 6 (+1) weeks, 3 (+1) months, 6 (+1) months and 12 months. Given that the ADAS-Cog is not used routinely in clinical practice (but rather a research assessment) and that the personnel involved may not necessarily be doing other studies requiring ADAS-Cog, it will not be possible to blind the professional doing the testing. The ADAS-Cog yields a single score that reflects the arbitrary weighting of performance in several cognitive domains including learning, language and spatial cognition but does not address executive function. A normal score for someone who does not have Alzheimer's or another type of dementia is 5; the greater

the dysfunction, the greater the score [59]. The properties of the ADAS-Cog are well understood; there is a curvilinear relationship between disease severity and rate of change on the ADAS-Cog. In a large clinical trial the baseline score for placebo-treated patients in the ADAS-Cog range of 13 to 26 was  $24.2 \pm 9.4$  and this increased to  $29.9 \pm 13.7$  representing a decline of  $5.7 \pm 8.2$  points over 1 year [60]. In this trial, a significant benefit in the active group was considered to be a 50% reduction in cognitive decline as indicated by change in ADAS-Cog score compared with the placebo group. In this study, patients who have an increase of no more than 50% (~3 points) on the ADAS-Cog at the end of treatment will be considered responders. This is equivalent to a delay in decline of about 6-8 months. Longitudinal analysis will be carried out for each individual patient using a fixed quadratic effect of time, dependent on the baseline level of ADAS-Cog, i.e., an interaction of baseline ADAS-Cog and the quadratic component of time.

The MMSE is a commonly used 30-point scale for assessing cognitive function in the domains of orientation, registration, attention and calculation, recall, language, and praxis. A MMSE score of 10 to 20 suggests moderate dementia. On average, the MMSE score of a person with moderate dementia declines about three to four points in a 12-month period. A similar analysis to that described above for the ADAS-Cog test will be carried out taking into account time and baseline MMSE score.

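### Stopping rule 5 cannot count an MMSE fall first seen at month 12, because no evaluation follows it; rule 6 masks this gap only as worded in section 3.12

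*Combined protocol and SAP*

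**What the plan says.** Rule 5 in section 3.12, repeated in the Schema, stops the study for "5 patients that show greater than 4 point deterioration in MMSE in two consecutive cognition evaluations". It names neither the reference score nor the denominator; rule 3 states 15 patients per group.

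Section 2.3 schedules the MMSE "at baseline and at 6 weeks, 3 months, 6 months, and 12 months during follow-up", and the Study Calendar agrees. The Schema gives the trial duration as "12 month follow up following completion of therapy for each individual". Section 2.3 also says that after radiation "the optimal time period for assessing cognitive impairment is within >6 months to 1 year".

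The stopping rules control escalation. According to the Schema, if after 12 months of follow-up "there have been no events that cause stoppage of the trial, the second group of patients will be enrolled at Dose Level 2". That level is 20 Gy, twice the first.

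Two statements bear on the size of the limit. Section 3.5 says that "a change of 4 or greater in the MMSE is needed before results can be considered different from random events". Section 3.10 says that, on average, "the MMSE score of a person with moderate dementia declines about three to four points in a 12-month period".

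Rule 6, the ADAS-Cog rule, is worded in two ways. Section 3.12 counts patients with increases above 7 points. The Schema counts "5 patients that show mean increases greater than 7 on ADAS-Cog scale".

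**The concern.** Rule 5 needs a pair of adjacent evaluations. The last available pair is months 6 and 12. A patient who is within the limit at month 6 and beyond it at month 12 has been seen beyond it once, and no later visit can confirm the fall. The MMSE rule thus cannot act on falls that are new in the very period that section 2.3 singles out.

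At stake is the decision to open 20 Gy. The same MMSE loss would almost surely stop the trial under this rule if it showed by month 6. If it arose abruptly after month 6, it would usually leave the rule silent.

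**Working it through.** **The plan's own figures.** The only statistical figures given for the design are the zero-event limits in section 3.1. They reproduce as 1 - (1 - confidence)^(1/15): 26.4% at 99%, 18.1% at 95% and 14.2% at 90%. No stop probability is given for any stopping rule.

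**Without variability.** At 4 points a year, natural decline is 2 points by month 6 and 4 by month 12.
- 5-point loss present by month 6: falls of 2 + 5 = 7 and 4 + 5 = 9. Both exceed 4, so the patient counts.
- 5-point loss after month 6: falls of 2 and 9. Only one exceeds 4, so the patient does not count.

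The stop probability is 1.00 against 0.00.

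**With variability.** Inputs from the documents: visits at 0, 1.5, 3, 6 and 12 months; baseline MMSE 10-20; decline 3 or 4 points a year; 15 patients. Assumed, because no MMSE SD is given: slope SD 2-3 points a year, visit-error SD 1-2, linear decline, whole-point scores, no dropout. The error range brackets section 3.5's 4-point noise limit: read as a 95% limit it gives 4/(1.96 x √2) = 1.44, and as a 90% limit 4/(1.645 x √2) = 1.72.

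Let p be the simulated chance that one patient is more than 4 points below baseline at two adjacent post-treatment visits. The rule stops with probability P(Bin(15, p) ≥ 5). Examples at 4 points a year, each cell showing p, then the stop probability:

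| Slope SD, error SD | 5-point loss by month 6 | 5-point loss after month 6 | No injury |
|---|---|---|---|
| 2, 1 | 0.913, 1.000 | 0.075, 0.004 | 0.069, 0.003 |
| 2, 1.44 | 0.840, 1.000 | 0.137, 0.044 | 0.118, 0.025 |
| 3, 2 | 0.732, 1.000 | 0.222, 0.225 | 0.191, 0.142 |
| 4, 2.5 (wider) | 0.665, 0.998 | 0.282, 0.421 | 0.244, 0.293 |

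Over the whole assumed range, excluding the wider row:

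| Scenario, all patients | P(stop), rule 5 alone |
|---|---|
| No injury | 0.00-0.15 |
| Abrupt 5 points by month 6 | 0.998-1.00 |
| Abrupt 5 points after month 6 | 0.00-0.24 |
| 5 points, linear from treatment to month 12 | 0.75-0.94 |
| 5 points, linear from month 3 to month 12 | 0.23-0.77 |

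Most of the 0.00-0.24 is natural decline and noise, as the no-injury row shows.

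**Rule 6.** Section 3.10 cites a one-year placebo change of 5.7 (SD 8.2). By normal approximation, P(rise > 7) = P(Z > (7 - 5.7)/8.2) = 0.437, and P(Bin(15, 0.437) ≥ 5) = 0.86 with no injury. An extra 7-point rise after month 6 takes this above 0.99.

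If the Schema's mean is a mean over the four post-treatment visits, a 7-point rise seen only at month 12 adds 7/4 = 1.75 points. With the month-12 SD held at 8.2 and an assumed visit-error SD of 0-5, the stop probability is 0.04-0.26 without injury, 0.32-0.59 with the late rise, and above 0.99 if the same rise is present from 6 weeks.

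**The case against.** **Rule 6 already stops the trial.** As worded in section 3.12 it needs no confirming visit and would usually stop a cohort with late injury. This stands. A reader might infer that rule 5's gap by itself lets 20 Gy open after a late injury; on section 3.12's wording that does not follow. But rule 6 also stops 0.86 of uninjured cohorts, so its stop does not separate injury from disease. The Schema's wording, on one possible reading, dilutes a late rise.

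**The contrast is a worst-case shape.** It assumes no loss through month 6, then the full loss in everyone. This stands. A reader might infer that a late loss almost never stops the trial; the gradual-loss figures, and the 0.24 itself, contradict that.

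**The result depends on the reading.** If falls are measured from the previous visit, the stop probability is about 0.01 even for an early loss and the contrast vanishes, but the rule is then nearly inert. If 5 points is the total change with no natural decline, the early figure is 0.79-0.92. Counting 5 of 30 would raise the late figure to as much as 0.83, but only 15 patients exist when escalation is decided.

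**Other month-12 protection exists.** Toxicity is graded at month 12 under rule 3, and section 3.9 sends a 2-point increase to the DSMB within a week. How cognitive decline would be graded is not defined, and the Appendix III worksheet has no cognitive item, so this cover is possible but not assured. A reader might also infer that the DSMB has no MMSE limit for month 12. That cannot be concluded: part of section 5.0 and the DSMB charter are not in the supplied text.

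**Confirmation is a reasonable safeguard.** With slope SD 2-4 and error SD 1.44-2, letting a single month-12 fall above 4 count would stop 0.49-0.90 of uninjured cohorts. This stands, and it is why the month-12 limit must allow for natural decline.

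**Conclusion.** The structural point follows from the text. Read as change from baseline, rule 5 cannot count a fall first seen at month 12.

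Its size rests on SDs that the protocol does not give, on natural decline of 3-4 points a year, on 15 patients and on no dropout. For an abrupt 5-point loss in all patients, the stop probability under rule 5 alone is above 0.99 by month 6 against 0.00-0.24 wholly after it, or about 0.42 at wider SDs. Losses that build up gradually lie between.

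The gap bears on escalation mainly under the Schema's wording of rule 6, or once rule 6 is set to allow for natural decline. It is worth closing because the change is cheap, not because the trial lacks all protection against late decline.

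**What to change.** In section 3.12 and the Schema, reword rule 5 to stop when at least 5 of 15 patients in either group are:
- (a) more than 4 points below their pre-treatment MMSE at each of two consecutive post-treatment evaluations; or
- (b) counted separately, more than 8 points below it at month 12.

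The 8 is the rule's own 4 points plus up to 4 points of natural yearly decline from section 3.10. The wording also settles the reference score and the denominator, and (b) is decided before dose level 2 opens.

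**Gain.** A late 5-point loss in all patients then stops the trial with probability about 0.82-0.99. The low end comes from decline of 3 points a year, where the average injured patient is 3 + 5 = 8 points down, exactly on the limit. With 25% of month-12 scores missing, the range is 0.53-0.86. That rate is plausible: in the appended ADAS instrument paper, 12-month word-list scores were missing for 7 of 47 patients with MMSE 16-20 and 16 of 45 with MMSE 10-15, or 23/92 = 25%.

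**Cost.** One clause in two places and no added visit. The uninjured stop probability under rule 5 rises from at most 0.15 to at most 0.17. With slope SD 4-5 it reaches 0.26-0.35, although rule 5 alone is already at 0.20 with slope SD 4 and error SD 2.

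Smaller late losses are still often missed: the stop probability is 0.07-0.69 for 3 points in all patients and 0.21-0.65 for 5 points in half. A limit of more than 7 would raise these to 0.39-0.89 and 0.51-0.83, with an uninjured stop probability of up to 0.25.
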